## Missing and Partial AE end dates:

- If end date is completely missing, end date is not imputed and the AE is flagged as "ongoing".
- If year is present and
  - month and day are missing:
    - If year = year of last dose, then set end date to the date of last dose.
    - If year < year of last dose, then set end month and day to December 31st.
    - If year > year of last dose, then set end month and day to January 1st.
  - month is missing:
    - If year = year of last dose, then set end date to date of last dose.
    - If year < year of last dose, then set end month to December.
    - If year > year of last dose, then set end month to January.
- If month and year are present and day is missing:
  - If year = year of last dose and
    - month = month of last dose then set day to day of last dose.
    - month < month of last dose then set day to last day of month.
    - month > month of last dose then set day to 1st day of month.
  - If year < year of last dose, then set end date to last day of the month.
  - If year > year of last dose, then set end date to 1st day of month.
- For all other cases, set end date to date of last dose.
- Screen failures are collected in EDC and will be a part of SDTM. Screen failure data
  are not analyzed and will not be included in the ADaM except for demographics
  (ADSL) and inclusion/exclusion criteria (ADIE).

Any AEs with incomplete start and end dates/times will be treated as follows:

• Adverse events with unknown start and/or end times (but where the date is known) will be imputed with a time of 00:00 h for the tabulations but will be shown as NK: NK in the listings (where NK = Not Known).

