# **6.2.** SAFETY FOLLOW-UP VISIT

All patients in Part A will have a final Follow-Up Visit at D182 ( $\pm 7$  days), 6 months after the single administration of ANK-700.

All patients in Part B will have a final Follow-Up Visit at D365 ( $\pm 14$  days), approximately 1 year after the first administration of ANK-700.

Ongoing AEs considered at least possibly related to ANK-700 treatment should be followed until resolution, return to baseline, or are considered stable or chronic.

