#### 6.1.1 Adverse Events (AE)

An AE is defined as any untoward medical occurrence associated with the use of a drug, or with study participation, whether or not consider related to study treatment. An AE can

therefore be any unfavorable and unintended sign (eg, an abnormal laboratory finding), symptom, or disease temporally associated with the use of the medicinal product, whether or not considered related to the medicinal product.

AEs include worsening of a pre-existing medical condition, including MS, as well as Clinically Significant (CS) changes from baseline laboratory values/conditions. Worsening of the preexisting medical condition (eg, diabetes, hypertension) means that it has increased in severity, frequency, and/or duration, and/or has an association with a significantly worse outcome. A pre-existing condition that has not worsened during the study is not considered an AE.

All AEs are collected from the time of signing of Informed Consent Form (ICF) through the final Follow-Up Visit/phone. Adverse events will be coded using the Medical Dictionary for Regulatory Activities (MedDRA) Version 23.1 (MedDRA Sep 2020) or higher. Ongoing AEs considered at least possibly related to ANK-700 treatment should be followed until resolution, return to baseline, or are considered stable or chronic.

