#### 10. DATA HANDLING AND MISSING DATA

All missing or partial data will be presented in the patient data listing, as they are recorded on the eCRF. Patients lost to follow-up or withdrawn will be included in statistical analyses up to the point of their last evaluation.

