## 10.1 Missing Start and Stop Dates/Time for Adverse Events

Due diligence will be done to obtain accurate AE information. If all planned methods to obtain accurate time AE information have failed, missing and partial AE onset and end dates will be imputed. Imputed dates will be flagged in the individual supportive patient listings. Unless otherwise specified, the following conventions will be used:

Missing and Partial AE onset dates:

- If onset date is completely missing, then onset date is set to date of first dose.
- If onset year is present and
  - month and day are missing:
    - If onset year = year of first dose, then set onset date to date of first dose.
    - If onset year < year of first dose, then set onset month and day to December 31st.
    - If onset year > year of first dose, then set onset month and day to January 1st.
  - month is missing:
    - If onset year = year of first dose, then set onset date to date of first dose.
    - If onset year < year of first dose, then set onset month to December.
    - If onset year > year of first dose, then set onset month to January.
- If onset month and year are present and day is missing:
  - If onset year = year of first dose and
    - onset month = month of first dose then set onset date to date of first dose.
    - onset month < month of first dose then set onset date to last day of month.
    - onset month > month of first dose then set onset date to 1st day of month.
  - If onset year < year of first dose, then set onset date to last day of month.
  - If onset year > year of first dose, then set onset date to 1st day of month.
- For all other cases, set onset date to date of first dose.

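### SAP 10.1 imputes partial AE end dates without checking them against onset, so listed end dates can precede the event or be cut short (minor, listings only)

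*SAP*

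**What the plan says.** SAP section 10.1, under the end-date rules, treats a partial AE end date as follows.

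- Day missing, same month as the last dose: "month = month of last dose then set day to day of last dose".
- Day missing, later month of the same year: "month > month of last dose then set day to 1st day of month".
- Day missing, later year: "If year > year of last dose, then set end date to 1st day of month".
- Only the year known, same year as the last dose: "If year = year of last dose, then set end date to the date of last dose". A later year gives 1 January.
- Month or year earlier than the last dose: the end of that period.
- Any remaining case: the date of last dose. A completely missing end is left as ongoing.

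No line in 10.1 compares the imputed end with the onset. Section 10.2 does contain a check of this kind, but only for medications: an imputed medication start must come before the end.

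The SAP also limits the damage. Section 10 states "All missing or partial data will be presented in the patient data listing, as they are recorded on the eCRF", and section 10.1 states "Imputed dates will be flagged in the individual supportive patient listings". Section 8.8.1 makes AE end date and AE duration columns of the listings.

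**The concern.** An early anchor is sensible for onset, where it protects classification as treatment-emergent. For an end date it works backwards. AEs are collected long after dosing stops: "All AEs are collected from the time of signing of Informed Consent Form (ICF) through the final Follow-Up Visit/phone", and "All patients in Part B will have a final Follow-Up Visit at D365" (D182 in Part A). Almost the whole AE window therefore lies after the last dose, and an AE in that window with a partial end date is usually pulled back towards the last dose or to the start of a month or year. Where onset is known more precisely than the end, the listing can show an event that ends before it begins. In other cases the event is shortened. At stake is whether the AE listings can be relied on, in a study whose primary objective is safety.

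**Working it through.** The plan states no figure on this point, so the check applies its rules directly.

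**Inputs.** Last dose is D1 in Part A and D7 in Part B (Protocol 4.3). Final visit is D182 or D365 (Protocol 6.2). The onset and end rules are those of SAP 10.1. Assumption: first-dose dates run over every day of 2021 and 2022 (730 dates). Each range below is the minimum and maximum over those dates of the number of onset days, from D1 to the final visit, on which the imputed end falls before onset. In cases (a) to (c) the imputed end does not depend on the true end day, so no assumption about AE duration is needed.

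**(a) Onset fully known; end in the onset month, day missing.** Days that escape inversion are those up to the last dose and the 1st of each later month.
- Part A: 1 day plus 5 or 6 month-firsts; 182 − 6 = 176, 182 − 7 = 175.
- Part B: 7 days plus 11 or 12 month-firsts; 365 − 18 = 347, 365 − 19 = 346.

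**(b) Onset fully known; end known only to the onset year.** Only the days up to the last dose and a later 1 January escape.
- Part A: 182 − 1 = 181, or 182 − 2 = 180.
- Part B: 365 − 7 = 358, or 365 − 8 = 357.

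**(c) Onset known to the month; end known only to the same year.** Onsets in the dosing month or in a later January escape, because both dates land on compatible anchors.
- Part A: 120-181 of 182 (66% to 99%). The low end is 182 − 31 − 31 = 120.
- Part B: 297-334 of 365 (81% to 92%). The low end arises when the three doses straddle two months: 365 − 6 − 31 − 31 = 297.

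**(d) Both dates lack the day, or both give only the year.** 0 inversions in both parts.

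**(e) Onset fully known; end in a later month than both onset and last dose, day missing.** 0 inversions. The end is set to the 1st, so it is 0 to 30 days early.

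**(f) AE resolved before the last dose.** Here the rule can be late.
- Part B, resolved between D1 and D7: up to 6 days late.
- Screening AE that ended 1 to 28 days before first dose, Part A: up to 28 days late.
- The same in Part B: up to 30 days late with the day missing (1st to 31st of one month), or 28 + 6 = 34 days late with only the year known.

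**Examples, last dose 10 March.**

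| Onset | Recorded end | Imputed end | Result |
|---|---|---|---|
| 12 April | April | 1 April | 11 days before onset |
| 12 June | year only | 10 March | 94 days before onset |
| June (imputed 1 June) | year only | 10 March | 83 days before onset |
| 10 March (Part A, true end 28 March) | March | 10 March | 18 days early |

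**Without the same-month condition.** Take the day as missing, onset as uniform over follow-up, a fixed AE duration and first-dose dates in 2022 (all assumptions). The share inverted is then 88-90% for 3-day AEs, 76-77% for 7-day, 53-54% for 14-day and 8% for 28-day. Inversion is mainly a problem of short events; longer ones are truncated.

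**The case against.** The strongest reply is that little depends on these dates. Imputation applies only after attempts to obtain the date have failed, and the number of affected AEs is unknown and may be small. The recorded partial date is still shown and the imputation is flagged. None of the AE tables in SAP 8.8.1 uses end date or duration. Section 8.1 has outputs independently checked for consistency, and an end before onset would be visible to such a check. The conventions also apply only where nothing else is specified.

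All of that stands as a limit on the harm. It does not rescue the rule: a general output check does not say which date to use instead, and nothing in 10.1 overrides the convention when it gives an impossible result.

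Three stronger readings are tempting, and the documents support none of them.
- A reader might infer that the primary endpoint is affected. Treatment-emergent status rests on when an AE emerges or worsens, and the summaries count patients by grade, relationship and seriousness.
- A reader might infer that dose-limiting toxicity calls are affected, because one criterion concerns Grade 2 events that do not resolve within 14 days. The SAP does not say that this status is derived from imputed ends, and the events go to the Safety Monitoring Committee during the study.
- A reader might take 175-176 of 182 to mean that nearly all AEs with partial dates are inverted, or that every end is too early. The counts are conditional on the end falling in the onset month or year, and case (f) runs in the other direction.

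**Conclusion.** The concern holds as a minor, listing-level error in a stated rule. Followed exactly, section 10.1 gives impossible end dates on nearly all possible onset days when onset is fully known and the end is known only to the same month or year. It does so on most, not nearly all, when onset is known to the month and the end only to the year. Elsewhere it shortens events, or lengthens those that resolved before the last dose. AE duration is affected only if it is computed from imputed dates, which the SAP does not state. The counts rest on the calendar years assumed for first dose and say nothing about how many AEs will have partial end dates.

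**What to change.** Amend section 10.1 in three places.

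1. Add a floor: an imputed AE end date is never earlier than the onset date, or the imputed onset date where onset is also partial. This is the essential correction.
2. Preferably, impute to the latest date the recorded part allows: the last day of a known month, or 31 December of a known year, capped at last contact or death. Section 10.2 already uses month end and 31 December for medication end dates, although for a different purpose. Applied to cases (a) and (b), this gives 0 inversions in both parts.
3. State whether listed AE duration uses imputed dates or is left blank when either date is partial.

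The cost is a few lines of SAP text and derivation code before database lock. The trade-off is that some ends will be late instead: by at most 30 days when only the day is missing, and up to year end or last contact when only the year is known.

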# 4.1. PART A – SINGLE ASCENDING DOSE

The SAD phase will include up to 3 cohorts with 3 patients each. Patients within each dose cohort will receive 1 dose of ANK-700 IV and will be monitored for up to 6 months. All patients in Part A will be dosed  $\geq$  14 days apart to monitor for acute and subacute reactions; this length of time is supported by nonclinical exposure data that suggest ANK-700 will have cleared > 5 half-lives and nonclinical animal model data demonstrating that the tolerance induction mechanism can develop and immunologically active peptide is cleared within 1 week from dosing (see Section 4.7 for more information).

Patients will arrive at the clinic on the morning of dosing (Day 1 [D1]) and will be monitored inclinic for 8 hours after completion of ANK-700 infusion for assessment of acute safety and PK blood sample collection. A follow up phone call 24 hours after dosing must be performed to ensure the patient did not experience any acute safety events after discharge.

- If patients are experiencing active AE(s) which require clinical monitoring at the end of the clinic/hospital unit monitoring period, they should not be discharged and followed up per PI assessment
- If feasible, patients should be advised to have someone stay with them after discharge until 24 hours have elapsed after study drug administration on D1.
- If patients do not live within 1-hour travel time of an emergency medical facility, they should remain in the clinic/hospital unit for the first 24 hours after study drug administration.
- Patients should be instructed not to drive themselves to seek emergency medical treatment at any time during the study.

Doses evaluated in Part A include 0.3 mg/kg (Cohort 1), 1.0 mg/kg (Cohort 2), and 3.0 mg/kg (Cohort 3). After all patients within a given dose cohort have been followed for ≥ 14 days post-dose, a safety review will be performed by the SMC to review all adverse events (AEs) and available clinical laboratory and PK data. Initiation of the next dose level will commence upon recommendation by the SMC and approval by the Sponsor.

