#### 4.7. Dose Escalation Safety Monitoring Period

In Part A, the dose-escalation safety monitoring period is from the beginning of the IV administration of ANK-700 through the D15 clinic visit. Any AEs that meet the criteria defined in Section 4.6 but occur after the dose-escalation safety monitoring period of Part A, may be considered by the SMC in the evaluation for Part B dose selection.

The dose-escalation safety monitoring period in Part B is from the beginning of the first IV administration of ANK-700/PBO through the D22 clinic visit.

The monitoring period is supported by nonclinical animal data, which demonstrate:

- ANK-700 is cleared from circulation in < 7 minutes, ensuring that > 5 half-lives have elapsed during the safety monitoring period
- T-cell tolerance induction can be observed as early as 1 week after drug administration in nonclinical models, ensuring the mechanism of action will be active and robust during the safety monitoring period
- Immunologically active antigen cannot be detected in animals 7 days after GP-peptide administration, ensuring that any processed antigen will be cleared during the safety monitoring period

AEs and any abnormal clinical parameters, including laboratory findings, observed during this period will be used by the SMC to determine whether dose escalation should proceed.

No patient with a DLT will be replaced.

In both parts, patients will be monitored in the clinic for 8 hours after the completion the first IV administration of ANK-700/PBO. In Part B, patients will be monitored in the clinic for 4 hours after completion of their second and third dose.

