## **6.1.2** Treatment Emergent Adverse Events (TEAE)

TEAEs are defined as AEs that emerge or worsen in the period from the first dose of study treatment to the final Follow-Up Visit/phone call after the last dose study drug. The incidence and severity of TEAEs as assessed by the CTCAE v5.0 or higher is considered the primary endpoint.

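### If treatment emergence is judged by date and time, the SAP's 00:00 rule places an untimed adverse event on the first dosing day before the infusion and outside the primary TEAE tables

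*SAP*

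**What the plan says.** The last rule in SAP 10.1 deals with adverse events whose date is known but whose clock time is not. Those "with unknown start and/or end times (but where the date is known) will be imputed with a time of 00:00 h for the tabulations". The imputed value is confined to tables, since the unknown times are not filled in for display: "but will be shown as NK: NK in the listings". The day of first dose is not treated separately.

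SAP 6.1.2 defines treatment-emergent events as "AEs that emerge or worsen in the period from the first dose of study treatment to the final Follow-Up Visit/phone call" and adds that the "incidence and severity of TEAEs as assessed by the CTCAE v5.0 or higher is considered the primary endpoint". Protocol 12.6 gives the same definition. Neither text says whether onset is compared with the first dose by calendar date or by date and time.

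On the timing of dosing, Protocol 4.1 states: "Patients will arrive at the clinic on the morning of dosing". Protocol 4.2 and SAP 2.3.2 say the same for Part B. Adverse events are collected from consent (SAP 6.1.1), onset time is among the fields listed, and a separate listing is planned for Non-TEAEs (SAP 8.8.1).

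For incomplete onset dates, SAP 10.1 leans the other way: "If onset date is completely missing, then onset date is set to date of first dose". Partial dates that could coincide with the first dose are also set to that date.

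**The concern.** Day 1 is when acute effects of a first-in-human infusion would be expected. An event known to have happened that day, but without a recorded time, is given the earliest possible minute of the day, hours before the infusion. Under a date-time flag it cannot then be treatment-emergent.

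The result would be odd by the SAP's own standards. An event with no onset date at all is moved to the date of first dose, while an event correctly dated to that day but lacking a time could be excluded. Two programmers following the same text could produce different counts for the primary endpoint.

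**Working it through.** The plan attaches no figure to this rule, so the check is of logic, followed by the effect of one patient.

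**Inputs**
- Imputed onset: Day 1, 00:00 (SAP 10.1).
- First dose: Day 1, after a morning arrival (Protocol 4.1 and 4.2). The hour is not given; 07:00 to 12:00 is assumed here, and any time after midnight gives the same answer.
- Group sizes: 8 in each Part B group, counting pooled placebo as one group (SAP 3.1); 3 in a Part A cohort, or 6 if expanded (SAP 2.3.1).

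**Step 1: classify an untimed Day 1 event**
- Date-time comparison (TEAE if onset date-time ≥ first-dose date-time): Day 1 00:00 precedes Day 1 07:00, 08:00, and so on to 12:00. The event is not a TEAE at any assumed hour.
- Date comparison (TEAE if onset date ≥ first-dose date): Day 1 equals Day 1. The event is a TEAE at every assumed hour.

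**Step 2: check the other dosing days**
- Day 4 and Day 7 at 00:00 both follow the Day 1 infusion. Untimed events on those days stay treatment-emergent under either comparison. The problem is confined to the day of first dose.

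**Step 3: ask what the imputed start time is for**
- The AE tables in SAP 8.8.1 are an overall summary and counts by system organ class and preferred term, severity, causality, maximum grade and seriousness. None uses duration or time to onset.
- AE duration appears only among the listing fields, and in listings the unknown time is not replaced by 00:00.
- The evident use of an imputed start time in these tables is therefore to place the event before or after the dose. This supports a date-time reading but does not prove it.

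**Step 4: effect of one displaced patient on incidence, 100 × 1/n**
- Part B group: 100 × 1/8 = 12.5 percentage points.
- Part A cohort: 100 × 1/3 = 33.3 points; if expanded, 100 × 1/6 = 16.7 points.

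For overall TEAE incidence, these shifts require the displaced event to be that patient's only TEAE in the whole follow-up. For a single row of the organ class or preferred term table, it need only be the patient's sole treatment-emergent event in that row, since SAP 8.8 counts a patient once per row.

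**The case against.** The strongest reply is that the flag may use calendar dates, in which case nothing is lost. Neighbouring rules work by date: the partial-date rules in SAP 10.1 compare year, month and day with the first-dose date, and SAP 8.3 classifies medications against that date. Setting ambiguous onsets to the first-dose date makes most sense with a date-level flag. This stands as a fair alternative reading, and it is why the conclusion is conditional. It does not remove the need to say so: SAP 8.3 names the date of first dose explicitly, whereas the TEAE definition does not.

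Four further limits also stand.
- The 00:00 rule literally covers known dates only. It reaches an onset date imputed to the first dose only if the programmer extends it.
- Untimed Day 1 events may be few. Protocol 4.1 and 4.2 provide 8 hours of observation and a call 24 hours after dosing, and SAP 10.1 requires due diligence before imputing. Events at home on the first evening, reported from recall, are the likeliest to lack a time.
- Placebo events are displaced in the same way, so the effect on a between-group difference depends on where the untimed events fall.
- A displaced event is still visible in the Non-TEAE listing.

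A reader might also infer that such events escape the dose-limiting toxicity window, because Protocol 4.7 runs the Part A window "from the beginning of the IV administration of ANK-700 through the D15 clinic visit". The documents do not support that inference. Protocol 4.6 and SAP 6.1.6 give the window in whole study days, D1 to D15 or D1 to D22, and Day 1 at 00:00 lies inside both. The SAP only lists dose-limiting toxicities, with the unknown time left unknown. The Safety Monitoring Committee acts on them during the study, not through a reporting imputation.

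**Conclusion.** The point holds conditionally. SAP 10.1 contains a stated rule that, under a date-time TEAE flag, removes every untimed event on the first dosing day from the primary endpoint tables, contrary to the SAP's own treatment of ambiguous onset dates. Under a date-level flag it has no effect, and the SAP does not say which applies.

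Within a group the rule can only lower TEAE counts. It does not follow that it always favours ANK-700 over placebo, because it applies equally to both. The shifts of 12.5, 33.3 and 16.7 points are per-patient effects under the only-TEAE condition, not forecasts; the number of affected events is unknown and could be zero. No effect on dose-limiting toxicity decisions is shown. What remains there is a difference in wording between Protocol 4.7 and the whole-day definition.

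**What to change.** Add to SAP 10.1 before database lock: an adverse event dated on the day of first dose with unknown start time is treatment-emergent (for example, by assigning it the start time of the first infusion) unless the record shows onset before the infusion, such as a stop time earlier than the infusion start. In SAP 6.1.2, state whether the TEAE flag compares dates or date-times. The 00:00 convention can stay for start times on other days.

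The cost is one or two sentences. The downside is that an occasional event that truly began before dosing on Day 1 would be counted as a TEAE, which is the cautious direction for a safety endpoint.

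Separately, the infusion-start wording in Protocol 4.7 and the whole-day window in Protocol 4.6 and SAP 6.1.6 should be reconciled.
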